### **Consent for Future Use of Data:**

The ICF for this research study states that de-identified research data will be shared with MIRROR /USU and the United States Army Special Operations Command (USASOC) and will be maintained indefinitely for possible use in future research. By consenting to participate in this research study, participants agree to allow us to maintain their de-identified research data indefinitely for possible use in future research.

Participants will not be given the option to opt out of us retaining their de-identified research data indefinitely for possible future use. The ICF states, "If you do not want your deidentified data collected as part of this research study to be kept for use in future research studies, you should not sign this consent form."

### **Long Term Data Storage & Access:**

The de-identified electronic dataset will be maintained by MIRROR/USU and the study team indefinitely or as long as it is practicable to maintain.

De-identified electronic research data will be securely transmitted from local study teams to the MIRROR /USU via REDCap or the DoD secure access file exchange (SAFE) application (or other permissible safe data sharing system). REDCap utilizes Secure Sockets Layer (SSL) in addition to other safeguards on its web server to maintain secure communication with end-users (see Appendix U). DoD SAFE uses a TLS (Transport Layer Security) protocol when files are uploaded and downloaded.

Once received, the electronic de-identified research data will be stored within an encrypted, access controlled, password protected electronic data capture and management system housed on a DoD-compliant server.

Access to the de-identified research data will be governed strictly on an individual-by-individual basis within the secure electronic data capture and management system. Individual data access as well as privileges will be clearly delegated, audited, and monitored by MIRROR/USU. Any future research using retained data will require a research protocol to be approved by an Institutional Review Board or other authorized official responsible for protecting human subjects of research.

We will also ask participants for permission to store their identifiable contact information for the purposes of being contacted to participate in future research studies. Participants will be provided the option to opt-in or opt-out of the storage of their contact information. All participants that opt in to the storage of contact information for the purposes of being contacted to participate in future research studies will have their name and contact information retained at study closure. The local study team will securely maintain the contact information indefinitely, or as long as it is practical to maintain. The PI will be responsible for ensuring secure storage and destruction, as applicable.

Any future research using retained data will require a research protocol to be approved by an Institutional Review Board or other authorized official responsible for protecting human subjects of research.

**Data Withdrawal from Storage:**

Participants may request to have their data withdrawn at any time before their personal identifiers have been removed. Once their data has been de-identified (when the study master list is destroyed at study closure), it will be impossible for the researchers to locate their specific study data.

Is this a data repository?

Yes  No

If Yes, provide the name of the Repository

USU OCIO REDCap

Who will have access to the Repository?

MIRROR/USU, study team members, and investigators, as appropriate

What data type will be stored in the Repository?

- Protected Health Information
- Limited Data Set
- De-identified Data

## 11.0 Statistical/Data Analysis Plan

### 11.1 Statistical Considerations:

List the statistical methods to be used to address the primary and secondary objectives, specific aims, and/or research hypotheses. Explain how missing data and outliers will be handled in the analysis. The analysis plan should be consistent with the study objectives. Include any subgroup analyses (e.g., gender or age group). Specify statistical methods and variables for each analysis. Describe how confounding variables will be controlled in the data analysis

Descriptive statistics will report location and scale in terms of mean and standard deviation for normally distributed variables, median and interquartile intervals for ordinal metric variables, and in terms of proportion and size for categorical variables. Descriptive statistics will be reported for baseline demographic and clinical characteristics at an overall level and by initial treatment group.

Outliers will be removed if determined to be erroneous based on relevant clinical expertise. Confounding will be principally controlled by randomization. In regards to the treatment of missing data, Oura Ring data will be analyzed despite presence of missing data at any point; with regards to non-continuous outcomes, data will be analyzed only if baseline and the 3-week follow-up are both present. In the event of missing data for a mid-point follow up (i.e., not baseline or the 3-week follow up), said patient will still be included in all models.

Statistical analyses will use generalized additive models predicting the change in outcome measures at 3 weeks relative to baseline for all measures except Oura Ring data. Oura Ring data will be aggregated by averaging readings across each 24-hour period and will be modeled using multi-level models incorporating random effects. Sensitivity analyses will be performed on longitudinal data for each outcome metric and will include multi-level models incorporating random effects as well as control variables to account for any differences explained by a selection of patient characteristics (such as body weight, etc.).

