#### **Appendix E Follow-Up Data Collection CRF:**

Collects relevant follow-up research data.

- VAS
- Borg Perceived Exertion Scale (3-week follow-up only)
- Elloumi fatigue scale (only at 3-week follow-up)
- CMJ
- Isometric/Isokinetic Strength (3-week follow-up only)
- Adverse Event (AE) assessment

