### 11.5 Please provide a justification for your sample size

Due to the accepted feasibility/pilot nature of this study, we understand that the proposed study may not be appropriately powered. Assuming a moderate effect size of .15 and a significance level of 5%; in the event we are able to enroll 116 participants (85 post-attrition) we will achieve 80% power. If we are able to enroll 135 participants (108 post-attrition), we will achieve 90% power. Power was calculated using the linear multiple regression module within G\*Power (Erdfelder, Faul, & Buchner, 1996).

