### 11.6 Data Analysis Plan: Complete description: Background, Objectives, Design, Step by Step how the project is going to be done, Data analysis plan:

Descriptive statistics will report location and scale in terms of mean and standard deviation for normally distributed variables, median and interquartile intervals for ordinal metric variables, and in terms of proportion and size for categorical variables. Descriptive statistics will be reported for baseline demographic and clinical characteristics at an overall level and by initial treatment group.

Statistical analyses will use generalized additive models predicting the change in outcome measures at 3 weeks relative to baseline for all measures except Oura Ring data. Oura Ring data will be aggregated by averaging readings across each 24-hour period and will be modeled using multi-level models incorporating random effects. Sensitivity analyses will be performed on longitudinal data for each outcome metric and will include multi-level models incorporating random effects as well as control variables to account for patient characteristics. Exact selection of control variables will be guided by observed differences within final collected data as well as relevant clinical expertise.

Hypothesis tests will be two-tailed and statistical significance will be considered at the putative threshold ( $\alpha=0.05$ ). Any secondary P-values will be subject to a false discovery rate adjustment in keeping with best statistical practices. Multilevel models will incorporate random effects to account for repeated measures, using distribution families and link functions appropriate for the outcomes of interest, determined using quantile-quantile (QQ) plots analyzed for best model fit. All statistical analyses will be performed using the R Programming language.

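### The 3-week value for DVPRS pain, rated daily, is not defined and most naturally means a single reading; a final-week mean with baseline as covariate would be more precise at almost no cost

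*Combined protocol and SAP*

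**What the plan says.** Section 10.1 (Follow-Up Data Collection) asks every participant to log activity and pain each day for three weeks. Section 10.2 puts a daily DVPRS in the activity log (Appendix F) and one DVPRS on the baseline form (Appendix D). Appendix E, described as a form that "Collects relevant follow-up research data", lists the soreness VAS, Borg, Elloumi, jump, strength and adverse events, but not DVPRS.

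Section 11.1, repeated in 11.6, specifies "generalized additive models predicting the change in outcome measures at 3 weeks relative to baseline for all measures except Oura Ring data". Oura readings are to be averaged over each 24 hours; no comparable rule is given for daily pain. Multi-level models of the longitudinal data are planned for each outcome as sensitivity analyses, and control variables are mentioned only there. For non-continuous outcomes, section 11.1 says that "data will be analyzed only if baseline and the 3-week follow-up are both present"; participants who miss only a mid-point visit stay in all models.

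**The concern.** A change score needs one number per man at three weeks. The log supplies about 21 daily ratings, and nothing says which of them, or which combination, is that number. This matters in three ways.

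- **Precision.** Pain on one day reflects that day's training and ordinary day-to-day variation. If one rating is used, the neighbouring ratings do nothing for the main pain estimate.
- **Missing data.** A man with 20 completed log days who skipped the chosen one would leave the main pain analysis. The both-values rule is limited to non-continuous outcomes and the plan does not say how DVPRS is classed, but a change score imposes the same requirement either way.
- **Latitude.** An undefined day or window can be settled after the data have been seen.

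The ratings are already paid for: under section 13.2 all three payments of $50 are tied to completing and returning the log.

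**Working it through.** **The plan's own figure.** Section 11.5 states: "in the event we are able to enroll 116 participants (85 post-attrition) we will achieve 80% power". The basis is "Assuming a moderate effect size of .15" in G*Power's linear multiple regression module. Reading 0.15 as f², with noncentrality 0.15 × N, a two-sided 5% level and an overall test of four predictors (the number is not stated), power is 80.3% at N = 85 and 90.1% at N = 108. Both stated figures reproduce. They are not tied to pain, so what follows does not bear on the sample size.

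**Inputs for the pain endpoint.** From the documents: one baseline rating (day 0) and daily ratings on days 1 to 21. Assumed: a 7-day window (days 15 to 21), equal variance on all days, and the correlation structures below.

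**Exchangeable days, correlation ρ, unit variance.**
- Single-day change: 2(1 − ρ).
- Change to a 7-day mean: (1 − ρ)(1 + 1/7) = (8/7)(1 − ρ).
- Ratio: (8/7)/2 = 0.571, a 43% reduction whatever the value of ρ. The single baseline rating keeps the gain from being larger.

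**Serially correlated days, AR(1) with parameter φ.**
- Single-day change (day 21): 2(1 − φ^21).
- Change to the 7-day mean: 1 + v − 2c, where v is the average of φ^|i−j| over days 15 to 21 and c is the average of φ^t over the same days.
- Example, φ = 0.5: v = 0.348 and c is negligible, so the ratio is 1.348/2 = 0.67.

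| φ | ratio | reduction |
|---|---|---|
| 0.3 | 0.62 | 38% |
| 0.5 | 0.67 | 33% |
| 0.7 | 0.76 | 24% |
| 0.8 | 0.81 | 19% |
| 0.9 | 0.84 | 16% |
| 0.95 | 0.83 | 17% |

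A stable person-level mean cancels from a change score, so the variance ratios also apply to AR(1) errors around such a mean.

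**Baseline as covariate, exchangeable days.** The residual variance ratio, 7-day mean against single day, both adjusted, is [(1 + 6ρ)/7 − ρ²]/(1 − ρ²). At ρ = 0.3 this is (0.400 − 0.090)/0.910 = 0.34; at 0.5 it is 0.43; at 0.7 it is 0.50.

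**What this means for power (illustration).** With 85/2 = 42.5 per arm, 80% power corresponds to d = (1.960 + 0.842) × √(2/42.5) = 0.61. With the same effect on all seven days, a 16% variance cut gives Φ(2.802/√0.84 − 1.960) = 86%, and a 43% cut gives Φ(2.802/√0.57 − 1.960) = 96%.

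**Missing entries (assumed independent).** If 10% of log days are missed, the single-day rule loses 10% of men. A rule needing 3 of 7 ratings loses P(at most 2 of 7 present) = 0.1⁷ + 7(0.9)(0.1⁶) + 21(0.9²)(0.1⁵) = 0.02%. At 20% missed the figures are 20% and 0.5%. A man who stops logging before the final week is lost under either rule.

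**If the effect is still building.** Suppose it grows linearly over 21 days. The mean effect over days 15 to 21 is then 18/21 = 0.857 of the day-21 effect, and 0.857² = 0.735. Relative efficiency becomes 0.735/0.571 = 1.29 for exchangeable days, 0.735/0.76 = 0.97 at φ = 0.7 and 0.735/0.84 = 0.88 at φ = 0.9. The gain shrinks, then disappears.

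**The case against.** The strongest reply is that the plan nowhere says one log day will be used. The 3-week visit in section 10.1 includes a follow-up questionnaire that is not itemised, the Appendix E entry in section 10.2 is a summary, and the Appendix K schedule is not in the text available. One day, a last-week mean or a visit item would all fit. This stands: a reader might infer that the plan prescribes a single log day, and it does not. But a DVPRS item at the visit would still be one reading, and an intended weekly mean would still need to be written down.

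A second reply is that the daily ratings are not thrown away, because the longitudinal sensitivity models would use them. That also stands, and the loss is confined to the main analysis. A sensitivity model does not, however, define the main endpoint.

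Third, 43% is not a figure from the documents. It needs a 7-day window, exchangeable days and an equal effect across the week. Soreness after repeated training may well be serially correlated, which lowers the gain, and section 10.1 continues treatment through week 3, so the effect may still be building.

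Fourth, pain is one of many outcomes, none is named primary, the aims are descriptive, and section 11.5 describes a pilot that may be underpowered. This limits the weight of the point but does not remove it.

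**Conclusion.** The point holds as a gap in definition with a cheap gain in precision attached. The main pain analysis has no stated 3-week value, and its most natural reading is a single rating. Against that reading, a final-week mean lowers change-score variance by about 43% with exchangeable days and by about 16% to 38% with serial correlation between 0.3 and 0.95. All of these rest on assumed correlation structures, a 7-day window and a similar effect across the final week. Protection against a missed entry is the second benefit; its size depends on an unknown skip rate.

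Two further inferences are not supported. The documents do not show that a fixed share of variance is being wasted, since they give no DVPRS standard deviation or correlation. Nor do they show that the sample size is wrong, since the power statement is generic and reproduces.

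**What to change.** In sections 11.1 and 11.6, define the 3-week DVPRS value as the mean of the last seven daily log ratings, with a stated minimum number present (for example three), and fit the main pain model with baseline DVPRS as a covariate. Keep the multi-level model of all daily ratings as the sensitivity analysis; it will also show whether the treatment difference is still changing during week 3. State the rule before treatment-group data are examined.

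The cost is about one sentence in each section and no new data. The endpoint becomes average pain over the final week rather than pain on one day. If the effect builds through that week, the mean understates the day-21 difference, and the precision gain may be small or nil.

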#### **Demographics, & Baseline Data Collection:**

Prior to receiving study treatment, participants will complete a Demographics CRF (Appendix C) which collects relevant demographics including: personal demography, military and employment demography, and study-specific demography.

Additionally, participants will complete a Baseline Data Collection CRF (Appendix D) that collects: relevant medical history, military & work status, validated self-report measures, and study-specific measures. The following study-specific measures will be collected by a study team member:

- Fitzpatrick Skin Phototype
- Height, weight, and body fat composition (measured by bioelectrical impedance with InBody 770)
- Measurements of the participant's quadriceps to calculate the appropriate PBMT dose. (See Appendix S for PBM dosing information).
- Assessments of both legs:
  - CMJ, assessing jump height, time to take-off, RSImod, Eccentric Deceleration Impulse, Countermovement Depth, Concentric Impulse, Movement Start to Peak Power, and any asymmetries, and
  - Isometric and isokinetic dynamometer testing, assessing isolated strength in the lower body (i.e., unilateral Peak Torque and Rate of Force Development of quadriceps and hamstrings).
  - Processes for these tests can be found in the Appendices L and W. CMJ data will be output from the Force Decks software and recorded directly by the study team to the Appendix D and E CRF tables at each test iteration.

Each participant will be assigned an Oura Ring at baseline. Participants will be instructed to wear the Oura Ring for the duration of the study. The Oura Ring will continuously measure sleep quality, heart rate, blood oxygen saturation percentage (SpO2) levels, and activity. Oura Ring data will be securely stored in OuraTeams with access only for research team members.

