#### THOR3 Coach-Lead Training

All participants will be enrolled in the THOR3 coach-lead training program as a standard daily exercise regimen, focusing on muscle strength, endurance, and stamina. This program will proceed without interference from the study. Activity during the THOR3 program will be documented (e.g., exercises, reps, etc.) on Appendix G THOR3 Training Program Log CRF. A study team member will export the training schedule from Bridge Athletic and will insert the information into Appendix G and ask the participant to confirm what training they completed.

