#### **Follow-Up Data Collection:**

Follow-up data will be recorded on Appendix E Follow-up Data Collection CRF.

Regardless of study arm assignment, all participants will be asked to log their daily activity and pain (Appendix F Activity Log CRF) and wear the Oura Ring for 3 weeks.

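### One 24-hour mean for all ring readings, with no sleep window or wear rule, makes ring heart rate (and SpO2, if continuous) insensitive to a sleep-time effect and dependent on when the ring was worn

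*Combined protocol and SAP*

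**What the plan says.** Section 10.1 (Demographics & Baseline Data Collection) describes the signals: "The Oura Ring will continuously measure sleep quality, heart rate, blood oxygen saturation percentage (SpO2) levels, and activity". The wear instruction there is "Participants will be instructed to wear the Oura Ring for the duration of the study", with no target for hours per day. The follow-up text in the same section sets the period at 3 weeks in both arms. Section 10.1 (THOR3 Coach-Lead Training) adds "All participants will be enrolled in the THOR3 coach-lead training program as a standard daily exercise regimen", so training falls inside the averaging window by design.

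Section 11.1 states the aggregation rule: "Oura Ring data will be aggregated by averaging readings across each 24-hour period". Section 11.6 repeats it together with the model: "Oura Ring data will be aggregated by averaging readings across each 24-hour period and will be modeled using multi-level models incorporating random effects". On missing data, Section 11.1 says "Oura Ring data will be analyzed despite presence of missing data at any point".

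The supplied text contains no sleep window, minimum wear time, valid-day definition, non-wear detection, wear-time covariate or separate rule per signal. The sensitivity models adjust for participant characteristics; body weight is the example given, and wear is not mentioned.

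**The concern.** Heart rate differs greatly between sleep, ordinary waking and hard training. A mean over the whole day has two weaknesses as a summary of it. First, if the treatment acts on resting or sleeping heart rate, the effect is diluted by the waking and training hours. Second, if the ring is off for part of the day, the mean is taken over a different mix of hours, and the daily value moves although the man's physiology has not.

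The study title includes recovery and Aim 1 concerns physiologic effects. The ring is the only continuous physiologic record in the trial, and it has its own model in the analysis plan. A null result on ring heart rate could therefore come from the summary chosen rather than from the absence of an effect.

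**Working it through.** **The plan's own figures.** None concerns the ring. The only design figures are in Section 11.5: 80% power with 85 evaluable and 90% with 108, for an effect size of 0.15 in linear multiple regression. Taking 0.15 as f², they reproduce with four predictors (0.803 and 0.901), a number the plan does not state. They play no part below.

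**Inputs from the documents.** One 24-hour mean for all ring readings (11.1, 11.6); continuous recording, daily training and 3 weeks of wear (10.1); a final sample of 85 (11.2).

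**Inputs assumed.** 8 h asleep at s = 50 to 55 bpm; training for t = 1 to 1.5 h at T = 120 to 140 bpm; the other 16 − t hours awake at w = 65 to 75 bpm; readings evenly spaced, since no sampling interval is given.

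**Dilution.** A change d confined to sleep moves a fully worn mean by d × 8/24. For d = 2 bpm this is 2 × 8/24 = 0.67 bpm.

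**Wear, one worked day** (s = 50, w = 70, T = 130, t = 1.5):
- Fully worn: (8×50 + 14.5×70 + 1.5×130)/24 = 1610/24 = 67.1 bpm.
- Off in training only: (400 + 1015)/22.5 = 62.9 bpm, a shift of −4.2.
- Worn only at night: 50.0 bpm, a shift of −17.1.

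The physiology is identical in all three.

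**Wear, over the assumed ranges.**
- Off in training: the fall is (t/24) × (T − m), where m = (8s + (16 − t)w)/(24 − t) is the mean without training. The smallest case is s = 55, w = 75, T = 120, t = 1: m = 1565/23 = 68.0 and the fall is (120 − 68.0)/24 = 2.2 bpm. The largest is s = 50, w = 65, T = 140, t = 1.5: m = 1342.5/22.5 = 59.7 and the fall is 1.5 × (140 − 59.7)/24 = 5.0 bpm.
- Night only: the fall is [(16 − t)(w − s) + t(T − s)]/24. The smallest case is s = 55, w = 65, T = 120, t = 1: (150 + 65)/24 = 9.0 bpm. The largest is s = 50, w = 75, T = 140, t = 1.5: (362.5 + 135)/24 = 20.7 bpm.

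**Effect on the arm comparison, by simulation.** The settings were 85 participants (43 and 42), 21 days and 3,000 runs, with participant means compared by arm as a simple stand-in for the planned model. All of the following are assumed: mean rates of 50, 72 and 135 bpm asleep, awake and training; between-person SD 6 bpm; day-to-day SDs 2, 3 and 8 bpm; nights worn 80% of the time on average; training on 3 days in 7, with the ring worn for half of sessions on average; a treatment effect on sleeping heart rate only.

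| Scenario | 24-hour mean: difference, rejection rate | Sleep-period mean: difference, rejection rate |
|---|---|---|
| No effect, equal wear | 0.0 bpm, 5% | 0.0 bpm, 6% |
| True effect −2 bpm, equal wear | −0.6 bpm, 8% | −2.0 bpm, 33% |
| True effect −4 bpm, equal wear | −1.1 bpm, 12% | −4.0 bpm, 85% |
| No effect, 10 points less night wear in one arm | +0.8 bpm, 9% | 0.0 bpm, 5% |
| No effect, 20 points less night wear in one arm | +1.6 bpm, 21% | 0.0 bpm, 6% |

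With equal wear the 24-hour mean keeps its type I error and loses power. With unequal wear it also shows a false difference.

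**The case against.** The strongest reply is that the design protects the comparison. Allocation is 1:1 at random, both arms follow the same training programme, and participants are blinded with a sham. This stands. Wear and training load unrelated to arm add noise and dilution but no bias, and nothing in the documents suggests that wear will differ by arm. The simulated type I error with equal wear agrees. A reader might infer that the ring comparison is biased; the text does not support that. What remains is lost sensitivity, and a plan with no check on wear by arm.

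Three other strong readings also fail.

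- A reader might take the missing-data sentence in 11.1 to mean that a partly worn day counts the same as a full one. In context it sits beside rules on which visits must be present, so it more naturally concerns who and which time points stay in the model. The plan gives no weights. Within-day non-wear is simply not addressed.
- A reader might infer that training load and wear are the main sources of day-to-day variation. The documents give no variance components, and the programme is described as daily for everyone, which weakens any contrast of training days with rest days.
- A reader might conclude that all ring outcomes are compromised. The arithmetic is for heart rate. It extends in kind to SpO2 if that is continuous, but no size is computed for it. A nightly sleep value is not mixed with waking or training. No section names a ring variable as a recovery endpoint; that link is an inference from the title and Aim 1.

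It can also be said that random effects deal with missing data. They accommodate missing days. They do not restore a daily mean taken over different hours, and a random intercept absorbs only a stable wear habit. The pilot status in Section 11.5 and the many other outcomes limit the importance of the point but do not remove it. Appendix K, the data collection schedule, is cited but was not available, so a wear rule there cannot be excluded; the analysis sections do not refer to one.

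**Conclusion.** The point holds for heart rate, and for SpO2 on the stated premise of continuous recording. A single 24-hour mean keeps about one third (8/24) of an effect confined to sleep. Under the assumed rates, wear alone moves it by 2.2 to 5.0 bpm (off in training) or 9.0 to 20.7 bpm (night only). The consequence is reduced sensitivity to a resting or sleep-time effect, with bias only if wear differs between arms.

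The mechanism and direction follow from the text. The sizes rest on assumed heart rates, hours and evenly spaced readings. The dilution also assumes that the effect is confined to sleep: an effect equal at all hours would pass undiluted into a fully worn 24-hour mean. The point is worth correcting because it is cheap. It does not touch the jump or strength outcomes.

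**What to change.** In Sections 11.1 and 11.6, replace the single rule by one rule per signal:

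- **Heart rate and SpO2:** mean over the recorded sleep period.
- **Sleep measures:** one value per night.
- **Valid night:** count a night only if it meets a pre-set minimum of recorded sleep. Four hours is an example without a source in the documents; the team should fix its own figure before unblinded analysis.
- **Activity:** analyse only days that meet a pre-set wear minimum, or adjust for wear time. Do not use an unadjusted daily total, which would count unworn hours as zero.
- **Reporting:** give wear time by arm, and keep the 24-hour mean as a sensitivity analysis, which also covers an effect spread over the day.

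The cost is protocol wording and some R code, with no added burden on participants. The downside is that some low-wear days and nights are excluded.
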